2.3.2. Known Potential Benefits

There are no known benefits attributable to the receipt of the M-001 vaccine, but there is the prospect of benefit. It is possible that vaccination with M-001 will prime the participant for

improved responses to future seasonal or pandemic influenza vaccines. Vaccination with IIV4 likely will lead to protection against seasonal influenza viruses.

There may be pandemic preparedness benefits to society in the future if the M-001 is shown to have a significant priming effect that leads to improved cellular immune responses to influenza and proves to be sufficiently safe so that it can be employed if a need for widespread vaccination against pandemic influenza virus strains occurs.

3. OBJECTIVES

3.1. Study Objectives

3.1.1. Primary Objectives

Safety

- To assess the safety as measured by vaccine related adverse events, reactogenicity, and laboratory adverse events of two doses of M-001 vaccine, each dose administered approximately 21 days apart

Immunogenicity

- To assess the T cell responses to M-001 component peptides following two doses of M-001

3.1.2. Secondary Objectives

Safety

- To assess all serious adverse events (SAEs) following receipt of each dose of M-001 vaccine or placebo, each dose separated by approximately 21 days, through the end of the study
- To assess all unsolicited non-serious AEs following receipt of each dose of M-001 or placebo, each dose separated by approximately 21 days, through 21 days after each dose of M-001 or placebo

Immunogenicity

- To assess the serum HAI and Neut antibody responses to the 2018-2019 IIV4 vaccine viruses

3.1.3. Exploratory Objectives

- To assess the IgG responses to the M-001 vaccine after receipt of placebo or two doses of M-001 vaccine and following receipt of licensed IIV4
- To assess the T cell responses to M-001 component peptides following one dose of M-001 or placebo
- To assess T cell responses to M-001 component peptides following receipt of licensed IIV4

- To assess the T cell cross-reactive responses to current seasonal influenza virus antigens and pandemic influenza virus antigens following each vaccination (M-001 and IIV4)
- To assess the longevity of T cell responses to M-001 peptides, seasonal influenza virus antigens and pandemic influenza virus antigens

3.2. Study Outcome Measures

3.2.1. Primary Outcome Measures

Safety

- Occurrence of vaccine-related SAEs from the time of the first study vaccination (M-001 or placebo) through approximately 6 months after the second M-001 study vaccination
- Occurrence of solicited injection site and systemic reactogenicity events on the day of each study vaccination through approximately 7 days after each M-001 vaccination
- Occurrence of clinical safety laboratory adverse events from the time of each study vaccination of M-001 through approximately 7 days after each M-001 vaccination

Immunogenicity

- Geometric Mean Percentage of T cell subsets expressing perforin, CD107a, IFN- γ , TNF- α , and IL2, alone or in combination, in CD4 and CD8 cells after stimulation with M-001 component peptides at baseline (Day 1) and 14 days after the second dose of M-001

3.2.2. Secondary Outcome Measures

Safety

- Occurrence of all SAEs, from the time of receiving the first M-001 or placebo study vaccination through the end of the study
- Occurrence of all unsolicited non-serious AEs from the time of first study vaccination through 21 days after each M-001 vaccination

Immunogenicity

- For HAI and Neuts, the percentage of subjects achieving seroconversion (defined as either a pre-vaccination titer <10 and a post-vaccination titer \geq 40 or a pre-vaccination titer \geq 10 and a minimum four-fold rise in post-vaccination antibody titer) to IIV4 vaccine viruses from Day 172 to Day 200
- For HAI and Neuts, the percentage of subjects with an antibody titer of 40 or greater and GMTs vs. IIV4 vaccine viruses on Days 1, 43, 172 and 200

3.2.3. Exploratory Outcome Measures

- Percentage of subjects achieving seroconversion (defined as a minimum four-fold rise in post-vaccination ELISA antibody titer) and GMTs of ELISA antibody vs. M-001 from Day 1 to Days 22, 43, 78, 172 and 200
- Geometric Mean Percentage of T cell subsets expressing perforin, CD107a, IFN- γ , TNF- α , and IL2, alone or in combination, in CD4 and CD8 cells after stimulation with M-001 peptides at baseline (Day 1) and approximately 14 days after one dose of M-001, 21 and 56 days following the second dose of M-001, and immediately prior to and 14 and 28 days after IIV4
- Percentage of T cell subsets expressing perforin, CD107a, IFN- γ , TNF- α , and IL2, alone or in combination, in CD4 and CD8 cells after stimulation with other influenza A antigens (including seasonal and pandemic influenza antigens) at baseline (Day 1), approximately 14 days after each study vaccination, 21 and 56 days following the second study vaccination and immediately prior to and approximately 14 and 28 days after IIV4
- Percentage of influenza-specific T cell memory subsets expressing discrete memory markers (CCR7, CD45RO, and CD57) at baseline (Day 1) and on study days 15, 36, 43, 78, 172, 186 and 200
- Percentage of influenza-specific CD4+ cell subsets expressing IL-4 or IL-17, T follicular helper cells (CD4+, CXCR5+, PD-1+, IL-21+), T follicular regulatory (Tfr) cells (CXCR5+, PD-1+, CD25+, CD1217+), and Tregs (CD25+, Foxp3+) at baseline (Day 1) and on study days 15, 36, 43, 78, 172, 186 and 200

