4. STUDY DESIGN

This is a Phase II randomized, double-blind, placebo-controlled trial in 120 males and non-pregnant females, 18 to 49 years old, inclusive, who are in good health and meet all eligibility criteria. This clinical trial is designed to assess the safety, reactogenicity, and immunogenicity of two priming doses of M-001 followed by administration of IIV4.

Subjects will be assigned randomly to 1 of 2 treatment arms (60 subjects per treatment arm) to receive two doses of the M-001 vaccine or placebo (saline) followed by a single dose of IIV4 (see Table 1). Group A will receive two doses of M-001, each containing 1 mg of M-001, on Days 1 and 22 followed by a single dose of IIV4 on approximately Day 172 (window for this visit ranges from Day 142 to Day 202). Group B will receive saline placebo on both Days 1 and 22, followed by a single dose of IIV4 approximately on Day 172.

Reactogenicity will be measured by the occurrence of solicited injection site and systemic reactions from the time of each study vaccination with M-001 (or placebo) through 7 days after the vaccination (inclusive of vaccination day). Unsolicited AEs will be collected from the time of each M-001 (or placebo) vaccination through approximately 21 days after each study vaccination. SAEs will be collected from the time of the first study vaccination through approximately 6 months after the second M-001 (or placebo) study vaccination. Clinical laboratory evaluations for safety will be performed on venous blood collected approximately 8 days after each M-001 (or placebo) vaccination (Days 9 and 30).

Immunogenicity testing will include performing HAI and Neut antibody assays on serum obtained immediately at baseline (Day 1) and on serum collected on Days 43, 172 and 200. ELISA antibody responses to the M-001 vaccine will be assessed on serum collected at baseline (Day 1) and on Days 22, 43, 78, 172 and 200. Cell-mediated immune responses to influenza antigens, including epitopes represented in the M-001 vaccine, and seasonal and candidate pandemic influenza viruses, will be assessed at baseline (Day 1), 14 days after each vaccination (Days 15, 36, and 186), approximately 21 days (Day 43) and approximately 56 days (Day 78) following receipt of the second M-001 (or placebo) dose, and immediately prior to and approximately 28 days after the IIV4 dose (Days 172 and 200).

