3.3. Study Definitions and Derived Variables

Geometric mean percentages (GMPs) are calculated as the product of the observed percentages raised to the 1/Nth root, where N is the number of observed values.

The baseline value for cellular and humoral immunity will be defined as the value obtained on Day 1 prior to M-001 vaccination.

M-001 antibody response after baseline will be summarized by GMTs and the proportion of subjects achieving seroconversion (defined as a minimum four-fold rise in post-vaccination ELISA antibody titer) at each time point, with corresponding 95% confidence intervals.

For individual subjects, fold rise will be calculated as the ratio of: $\frac{post-vaccination\ titer}{pre-vaccination\ titer}$, where pre-vaccination value is always the result obtained at Day 1, prior to the first M-001 dose.

Seroconversion for HAI and Neut assays is defined as either a pre-vaccination titer < 1:10 and a post-vaccination titer $\ge 1:40$, or a pre-vaccination titer $\ge 1:10$ and a minimum four-fold rise in post-vaccination titer.

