8.3. Exploratory Immunogenicity Analyses

ELISA seroconversion and GMTs of the ELISA antibody against M-001 from Day 1 to Days 22, 43, 78, 172, and 200 will be presented in Table 44.

Table 26Table 27Table 28Table 29

These percentages will be summarized visually in box plots over time in Figure 6, Figure 7, Figure 8, and Figure 9, for selected cell subsets.

GMPs of influenza-specific CD4+ T cell subsets expressing discrete memory markers (CCR7, CD45RO, and CD57) will be summarized at baseline (Day 1) and on study days 15, 36, 43, 78, 172, 186, and 200 (Table 38), by study arm. The subject-level percentages corresponding to selected cell subsets will be presented in Figure 30. Analogous summaries will be presented for CD8+ T cells in Table 39and Figure 31.

The percentage of influenza-specific CD4+ cell subsets expressing IL-4 or IL-17, T follicular helper cells (CD4+, CXCR5+, PD-1+, IL-21+), T follicular regulatory (Tfr) cells (CXCR5+, PD-1+, CD25+, CD127+), and Tregs (CD25+, Foxp3+) measured by flow cytometry will be summarized at baseline (Day 1) and on study days 15, 36, 43, 78, 172, 186, and 200 (Table 40, Table 41, Table 42, and Table 43, respectively). Boxplots for these percentages will also be presented in Figure 32, Figure 33, Figure 34, and Figure 35.

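### ELISA seroconversion at Day 200 is counted from Day 1, so in the M-001 arm it is a cumulative response and does not by itself isolate the IgG response to IIV4; a paired Day 172 to Day 200 change would.

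*Protocol*

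**What the plan says.** Protocol 3.1.3, repeated in SAP 3.1.3, sets the objective: "To assess the IgG responses to the M-001 vaccine after receipt of placebo or two doses of M-001 vaccine and following receipt of licensed IIV4". It has two parts, one for the M-001 or placebo series and one for IIV4.

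The matching outcome in Protocol 3.2.3 is the percentage seroconverting, "defined as a minimum four-fold rise in post-vaccination ELISA antibody titer", together with "GMTs of ELISA antibody vs. M-001 from Day 1 to Days 22, 43, 78, 172 and 200". SAP 8.3 plans the same: "ELISA seroconversion and GMTs of the ELISA antibody against M-001 from Day 1 to Days 22, 43, 78, 172, and 200". SAP 3.3 states the reference for fold rise without exception: "where pre-vaccination value is always the result obtained at Day 1, prior to the first M-001 dose".

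In Protocol Section 4, Group A receives M-001 "on Days 1 and 22 followed by a single dose of IIV4 on approximately Day 172". The same section has the ELISA run on serum from Days 1, 22, 43, 78, 172 and 200. Protocol 7.2.8 has the Visit 9 antibody sample drawn before IIV4 is given.

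SAP Table 44 lists, by arm and day, the GMT and the seroconversion percentage, each with a 95% CI. Days 172 and 200 are adjacent rows, and there is no column for the change between them. For HAI and Neut, Protocol 3.2.2 and 11.5.3 count seroconversion from Day 172 to Day 200.

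**The concern.** By Day 200 a Group A subject has had three vaccinations, two of M-001 and one of IIV4. A rise counted from Day 1 adds up all three. A subject who is still four-fold above Day 1 just before IIV4, and who holds that level, is a Day 200 seroconverter whatever IIV4 did. A subject already past the four-fold mark who then rises further after IIV4 adds nothing to the rate. Group B received saline and carries no antibody induced by M-001, so the arms are expected to differ on this measure before IIV4 is given.

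What is at stake is how one exploratory result is read. Protocol 11.5 places ELISA data through Day 200 in a topline report intended for planning later trials and possibly for publication. In a prime-and-boost study, a gap between arms in the Day 200 rate, read without the Day 172 row, could be taken for a primed response to IIV4.

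**Working it through.** The documents state no ELISA seroconversion rate, power or sample size, so there is no ELISA figure to reproduce. The planned size is 60 per arm (Protocol 11.3.4).

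**Step 1. Arithmetic on the definition, with no assumptions.** Titers are expressed as multiples of the subject's Day 1 value.

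| Group A subject | Day 172 | Day 200 | Seroconverted at Day 200, from Day 1 | Rise from Day 172 |
|---|---|---|---|---|
| Holds level | 8 | 8 | Yes (8 ≥ 4) | 8/8 = 1-fold |
| Boosted | 4 | 16 | Yes, and already counted at Day 172 | 16/4 = 4-fold |

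The Day 1-based rate treats these two alike at Day 200. A Day 172 reference separates them.

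**Step 2. How large the carry-over could be.** All inputs in this step are assumptions. Let r be the geometric mean fold over Day 1 still present at Day 172, k the true fold rise from IIV4, s the between-subject SD of log10 fold at Day 172, and w the SD of the log10 change from Day 172 to Day 200. Then:

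- P(four-fold from Day 1) = 1 − Φ[(log10 4 − log10 r − log10 k)/√(s² + w²)]
- P(four-fold from Day 172) = 1 − Φ[(log10 4 − log10 k)/w]

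Take w = 0.2 and s = 0.3 to 0.5. For r = 1, k = 1, s = 0.3, the first formula has argument 0.602/√(0.09 + 0.04) = 0.602/0.361 = 1.67, giving 5%. The second has 0.602/0.2 = 3.01, giving 0.1%. The full set is:

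| r | From Day 1, k = 1 | From Day 1, k = 4 | From Day 172, k = 1 | From Day 172, k = 4 |
|---|---|---|---|---|
| 1 | 5–13% | 50% | 0.1% | 50% |
| 2 | 20–29% | 71–80% | 0.1% | 50% |
| 4 | 50% | 87–95% | 0.1% | 50% |
| 8 | 71–80% | 95–99% | 0.1% | 50% |

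The Day 1-based rate moves with r. The Day 172-based rate moves only with k.

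**Step 3. A second set of assumed inputs.** Suppose a mean rise of 8- to 32-fold at Day 43 (3 to 5 log2), a 2- to 4-fold fall by Day 172 (1 to 2 log2), log2 SD 1.5, and no IIV4 effect. The mean residual is then 3 − 2 = 1 to 5 − 1 = 4 log2, against a threshold of 2 log2. The Day 200 rate from Day 1 runs from 1 − Φ[(2 − 1)/1.5] = 25% to 1 − Φ[(2 − 4)/1.5] = 91%. Simulation with small assay noise gave 26% to 90%, and about 0% counted from Day 172. The two sets together span about 5% to 90%.

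**Step 4. What Table 44 can and cannot give.** In a fixed set of subjects, GMT at Day 200 divided by GMT at Day 172 equals the geometric mean fold rise, so the point estimate can be read off. Its CI cannot, because the variance of the paired change is Var(200) + Var(172) − 2 Cov(172, 200) on the log scale, and the table carries no covariance. The sets may also differ. SAP 6.3.2 and Table 14 define per-protocol membership visit by visit, and Day 200 adds exclusions for a missed or out-of-window third vaccination and for its own result and visit window.

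**The case against.** The strongest reply is that the plan already shows the ELISA on either side of IIV4. Table 44 prints GMT and seroconversion at Day 172 directly above Day 200, by arm and with CIs. Protocol 11.5.3 mentions longitudinal GMT plots, and Listing 16 gives individual titers. If IIV4 did nothing, the M-001 arm would show similar rates on both rows and a careful reader would see the carry-over. A boost in subjects already counted would show in the GMT column. All of this stands. A reader might infer that the trial cannot show the IgG response to IIV4 at all, but the documents do not support that. What is missing is the paired change and its CI.

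A second reply is that the objective can be read as asking for the level reached after IIV4 in the prime-and-boost sequence, for which Day 1 is a fair reference. The HAI/Neut comparison is also imperfect, because those assays target the IIV4 strains and this one targets M-001, first given on Day 1. That reading is tenable. It is the reason to keep the Day 1-based figure, but it does not remove the value of the Day 172 contrast.

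A third reply concerns size. The percentages come from assumed inputs, and the near-zero rate from Day 172 follows from setting the IIV4 effect to none with little assay noise. This also stands. A reader might further infer a placebo rate of about 0 at Day 200. The documents do not establish it: Protocol 2.1.2 describes the M-001 epitopes as common to most influenza strains, and the months between Day 1 and Day 172 leave room for natural exposure.

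**Conclusion.** The point holds in a limited form. ELISA seroconversion at Day 200 in the M-001 arm is cumulative over M-001 and IIV4, and the rate alone does not isolate the IIV4 part of the objective. Under the "pre-vaccination value is always the result obtained at Day 1, prior to the first M-001 dose" rule, no Day 172 to Day 200 ELISA change is defined in either document, although both samples are taken and assayed. The existing Day 172 and Day 200 rows allow a descriptive comparison but no paired estimate with a CI.

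The range of about 5% to 90% illustrates dependence on persistence and does not predict the trial's result. The endpoint is exploratory, no between-arm ELISA test is planned, and the primary, secondary and safety conclusions are untouched. The point is minor and the change optional, but worth making because the data will already exist.

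**What to change.** In SAP 3.3, 8.3 and Table 44, with the outcome measure in Protocol and SAP 3.2.3 aligned, add for subjects with both a Day 172 and a Day 200 ELISA result, by arm:

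- the geometric mean fold rise Day 200/Day 172 with 95% CI;
- the percentage with at least a four-fold rise from Day 172 to Day 200, with an exact 95% CI.

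State the number of pairs. Limit the Day 1 rule in SAP 3.3 so that it does not govern this contrast. Keep the Day 1-based Day 200 figure and label it as cumulative over M-001 and IIV4. An M-001:placebo ratio of the fold rises is optional.

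Two related wording problems can be settled in the same edit. The Day 1 rule as written also clashes with the Day 172 to Day 200 HAI/Neut seroconversion in Protocol and SAP 3.2.2. The Table 44 footnote gives the HAI-type seroconversion definition, while Protocol 3.2.3 and SAP 3.2.3 and 3.3 define ELISA seroconversion by the four-fold rise only.

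The cost is a few sentences across these sections, extra columns or a short panel in Table 44, and a little programming. No new visits, samples or assays are needed.

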4. STUDY DESIGN

This is a Phase II randomized, double-blind, placebo-controlled trial in 120 males and non-pregnant females, 18 to 49 years old, inclusive, who are in good health and meet all eligibility criteria. This clinical trial is designed to assess the safety, reactogenicity, and immunogenicity of two priming doses of M-001 followed by administration of IIV4.

Subjects will be assigned randomly to 1 of 2 treatment arms (60 subjects per treatment arm) to receive two doses of the M-001 vaccine or placebo (saline) followed by a single dose of IIV4 (see Table 1). Group A will receive two doses of M-001, each containing 1 mg of M-001, on Days 1 and 22 followed by a single dose of IIV4 on approximately Day 172 (window for this visit ranges from Day 142 to Day 202). Group B will receive saline placebo on both Days 1 and 22, followed by a single dose of IIV4 approximately on Day 172.

Reactogenicity will be measured by the occurrence of solicited injection site and systemic reactions from the time of each study vaccination with M-001 (or placebo) through 7 days after the vaccination (inclusive of vaccination day). Unsolicited AEs will be collected from the time of each M-001 (or placebo) vaccination through approximately 21 days after each study vaccination. SAEs will be collected from the time of the first study vaccination through approximately 6 months after the second M-001 (or placebo) study vaccination. Clinical laboratory evaluations for safety will be performed on venous blood collected approximately 8 days after each M-001 (or placebo) vaccination (Days 9 and 30).

Immunogenicity testing will include performing HAI and Neut antibody assays on serum obtained immediately at baseline (Day 1) and on serum collected on Days 43, 172 and 200. ELISA antibody responses to the M-001 vaccine will be assessed on serum collected at baseline (Day 1) and on Days 22, 43, 78, 172 and 200. Cell-mediated immune responses to influenza antigens, including epitopes represented in the M-001 vaccine, and seasonal and candidate pandemic influenza viruses, will be assessed at baseline (Day 1), 14 days after each vaccination (Days 15, 36, and 186), approximately 21 days (Day 43) and approximately 56 days (Day 78) following receipt of the second M-001 (or placebo) dose, and immediately prior to and approximately 28 days after the IIV4 dose (Days 172 and 200).

The duration of this trial for each subject will be approximately 7 months. If visit 11 occurs before Study Day 200 (because Visit 9 occurred prior to Day 172 and moved visits 10 and 11 to earlier times after study start), then an additional study visit (Visit 12, phone call) will occur on Day 200 to solicit SAE information.

For additional details on study procedures and evaluations and study schedule by study visits/days, see [Sections 7 and 8](#) and [Appendix A: Schedule of Study Procedures and Evaluations](#).

5. STUDY ENROLLMENT AND WITHDRAWAL

5.1. Subject Inclusion Criteria

Subjects eligible to participate in this study must meet all of the following inclusion criteria:

1. Provide written informed consent prior to initiation of any study procedures.
2. Are able to understand and comply with planned study procedures and be available for all study visits.
3. Are males or non-pregnant females, 18 to 49 years old, inclusive.
4. Are in good health*.

As determined by medical history and targeted physical examination to evaluate acute or currently ongoing chronic medical diagnoses or conditions, defined as those that have been present for at least 90 days, which would affect the assessment of the safety of subjects or the immunogenicity of study vaccinations. Chronic medical diagnoses or conditions should be stable for the last 60 days prior to investigational vaccine study product administration. This includes no change in chronic prescription medication, dose, or frequency as a result of deterioration of the chronic medical diagnosis or condition in the 60 days prior to enrollment and investigational vaccine study product administration. Any prescription change that is due to change of health care provider, insurance company, etc., or that is done for financial reasons, as long as in the same class of medication, will not be considered a deviation of this inclusion criterion. Any change in prescription medication due to **improvement of a disease outcome, as determined by the site principal investigator or appropriate sub-investigator, will not be considered a deviation of this inclusion criterion. Subjects may be on chronic or as needed (prn) medications if, in the opinion of the site principal investigator or appropriate sub-investigator, they pose no additional risk to subject safety or assessment of reactogenicity and immunogenicity and do not indicate a worsening of medical diagnosis or condition. Similarly, medication changes subsequent to enrollment and investigational study product vaccination are acceptable provided there was no deterioration in the subject's chronic medical condition that necessitated a medication change. All chronic medical conditions should pose no additional risk to the subject or interference with the evaluation of responses to study vaccination. Note: Topical, nasal, and inhaled medications (with the exception of inhaled corticosteroids as outlined in the Subject Exclusion Criteria (see Section 5.2), herbals, vitamins, and supplements are permitted.*

5. Oral temperature is less than 100.0°F.
6. Pulse[†] is 50 to 100 bpm, inclusive.

†Acceptable pulse range prior to IIV4 dose is 45 to 115 bpm, inclusive and no symptoms.

7. Systolic blood pressure[‡] is 85 to 150 mm Hg, inclusive.

‡Acceptable systolic blood pressure range prior to IIV4 dose is 80 to 155 mm Hg, inclusive and no symptoms.

8. Diastolic blood pressure^{**} is 55 to 95 mmHg, inclusive.

***Acceptable diastolic blood pressure range prior to IIV4 dose is 50 to 100 mm Hg, inclusive and no symptoms.*

9. Women of childbearing potential[‡] must use an acceptable method of contraception[§] from 30 days prior to vaccination until 60 days after the second of dose of M-001 or placebo.
10. Women of childbearing potential[‡] must use an acceptable method of contraception[§] from 30 days prior to receipt of IIV vaccination, and must plan to use until 28 days after the IIV.

‡Not sterilized via tubal ligation, bilateral oophorectomy, hysterectomy, or successful Essure[®] placement (permanent, non-surgical, non-hormonal sterilization with history of documented radiological confirmation test achieved or with

use of another approved birth control method if confirmation test not confirmed) and still menstruating or < 1 year of the last menses if menopausal).

§Includes, but is not limited to, non-male sexual relationships, abstinence from sexual intercourse with a male partner, monogamous relationship with a vasectomized partner, male condoms with the use of applied spermicide, intrauterine devices, NuvaRing®, and licensed hormonal methods such as implants, injectables, contraceptive patches or oral contraceptives (“the pill”). Method of contraception will be captured on the appropriate data collection form.

11. Female subjects of childbearing potential must have a negative urine or serum pregnancy test within 24 hours prior to study vaccination.

